11.2 Assessment of Adverse Events

All AEs and SAEs whether volunteered by the participant, discovered by study personnel during questioning, or detected through physical examination, laboratory test, or other means will be reported appropriately. Each reported AE or SAE will be described by its duration (i.e., start and end dates), regulatory seriousness criteria if applicable, suspected relationship to the study drug (see following guidance), and actions taken. To ensure consistency of AE and SAE causality assessments, only the PI or physician sub-investigators may grade AEs, and investigators should apply the following general guideline:

11.2.1 Relationship to study drug: Yes

There is a plausible temporal relationship between the onset of the AE and administration of the study drug, and the AE cannot be readily explained by the participant's clinical state, intercurrent illness, or concomitant therapies; and/or the AE follows a known pattern of response to the study drug; and/or the AE abates or resolves upon discontinuation of the study drug or dose reduction and, if applicable, reappears upon re-challenge.

11.2.2 Relationship to study drug: No

Evidence exists that the AE has an etiology other than the study drug (e.g., preexisting medical condition, underlying disease, intercurrent illness, or concomitant medication); and/or the AE has no plausible temporal relationship to study drug administration (e.g., cancer diagnosed 2 days after first dose of study drug).

Expected adverse events are those adverse events that are listed or characterized in the Package Insert.

Unexpected adverse events are those not listed in the Package Insert. This includes adverse events for which the specificity or severity is not consistent with the description in the Package Insert. For example, under this definition, hepatic necrosis would be unexpected if the Package Insert only referred to elevated hepatic enzymes or hepatitis.

11.2.3 Diagnosis vs. Signs and Symptoms

If known at the time of reporting, a diagnosis should be reported rather than individual signs and symptoms (e.g., record only liver failure or hepatitis rather than jaundice, asterixis, and elevated transaminases). However, if a constellation of signs and/or symptoms cannot be medically characterized as a single diagnosis or syndrome at the time of reporting, it is ok to report the information that is currently available. If a diagnosis is subsequently established, it should be reported as follow-up information.

11.2.4 Deaths

All deaths that occur during the protocol-specified AE reporting period (see Section 12.1), regardless of attribution, will be reported to the appropriate parties. When recording a death, the event or condition that caused or contributed to the fatal outcome should be reported as the single medical concept. If the cause of death is unknown and cannot be ascertained at the time of reporting, report "UnexplainedDeath".

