Coronaviruses are a large family of viruses that commonly infect many animals, including camels, cattle, cats, and are often found in bats as their zoonotic reservoir. While it is rare, animal coronaviruses can infect people and then spread between people, as had occurred with Middle East respiratory coronavirus (MERS-CoV) and severe acute respiratory coronavirus (SARS-CoV), and now the newly emerged coronavirus SARS-CoV-2 (also known as COVID-19). The SARS-CoV-2 virus is a betacoronavirus, like MERS-CoV and SARS-CoV. All three of these viruses have their origins in bats. While SARS-CoV and MERS-CoV exhibit significantly higher mortality than SARS-CoV-2, the ability to spread between humans is less than SARS-CoV-2. There is emerging evidence from Asia that patients can be highly contagious with one patient spreading viral particles to 87% of 15 sites within the patient's room. Virus can be shed in urine and feces as well as respiratory secretions increasing the likelihood that sick contacts and hospital staff will become infected (2). An epidemiological survey of 72,000 cases in China found and overall 3.8% infection rate in hospital workers, but a 68% infection rate of hospital workers in Wuhan at the epicenter of disease. This suggests that if low rates of infection are in a community, the likelihood of hospital workers contracting disease is low, but if there are a large number of cases then the likelihood of hospital workers contracting the disease is high (3). Patients above the age of 50 are more likely to die of this disease and the time from diagnosis to death can occur within one month despite access to high-level intensive care units (4). A high rate of intra-family transmission and rapid community transmission has been documented in Shenzhen China (5). Meanwhile a screen of compounds found that chloroquine prevented and

The PATCH Trial

irradiated established infection of SARS-CoV-2 virus in vitro. The Chinese and Korean consensus guidelines for COVID-19 treatment include chloroquine. However, based on our experience in cancer clinical trials we believe hydroxychloroquine is a safer drug than chloroquine and affords the ability to dose escalate to concentrations that we know are effective at blocking the lysosome in patients. A recent study found that hydroxychloroquine produced rapid clearance of virus in hospitalized patients with COVID-19 (Gautret et al Int. J Antimicrobial Agents 2020 in press).

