10.3 Off treatment/Off Study

Each participant has the right to withdraw from the study at any time without prejudice. The investigator may discontinue any person's participation for any reason, including adverse event or failure to comply with the protocol. Should a participant withdraw from the study, the reason(s) must be stated on the case report form, and a final evaluation of the participant should be performed. Reasons for withdrawal include the following:

Progression of Disease: Remove participant from protocol therapy at the time progressive disease is documented. Progression of disease is left to the discretion of the treating physician/ sub-Investigator; however, the following guidelines are provided to help decision making for discontinuing study drug:

Sub-study 1: Progression of disease can be confirmed if there is increase in COVID-19 symptom score for 2 days in a row and is three points higher than baseline. Once criteria for release from quarantine is met in SS1 the patient is off study. Once the person is hospitalized for COVID-19 in sub-study 1 the subject is off study. Participants who have progressive symptoms and are subsequently hospitalized as related to COVID-19 will not be crossed over to receive HCQ at the time of unblinding.

Sub-study 3: Development of new symptomology consistent with COVID-19: e.g. fever, cough, shortness of breath and SARS-COV2 test positivity would lead to unblinding. If on placebo the subject can crossover to HCQ for treatment and stay on study for 14 days or release from quarantine. If the subject was on HCQ the subject is off study and will be instructed to seek medical attention through their primary care physician

Extraordinary Medical Circumstance: If at any time the treating physician feels constraints of this protocol are detrimental to the participant's health remove the participant from protocol therapy.

Participant's refusal to continue treatment: In this event, document the reason(s) for withdrawal.

Failure to comply with protocol (as judged by the investigator such as compliance below 80%, failure to maintain appointments, etc.).

Withdrawal from treatment per patient choice: Patients may withdraw from study treatment at any point in the study for any reason. These subjects are allowed to withdraw from treatment but continue to participate with any of the other study procedures for the intended 2 month period.

Delay in treatment > 7 days due to toxicity

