11.0 ADVERSE EVENTS AND REPORTING

The timely reporting of adverse events (including toxic deaths) is required by the Food and Drug Administration. The reporting of toxicities is part of the data reporting for this study. The sponsor-investigator is responsible for ensuring that all adverse events (AEs) and serious adverse events (SAEs) that are observed or reported during the study are collected. Misuse and abuse of the study medication, medication errors and uses outside of what is foreseen in the protocol (irrespective if a clinical event has occurred) must be reported within 24 hours to the Study Sponsor/ Principal Investigator.

Adverse Events

Property of University of Pennsylvania
Confidential

The PATCH Trial

An **adverse event** (AE) is any symptom, sign, illness or experience that develops or worsens in severity during the course of the study that does not necessarily have a causal relationship with this treatment. Intercurrent illnesses or injuries should be regarded as adverse events. Abnormal results of diagnostic procedures are considered to be adverse events only if the abnormality:

- results in study withdrawal
- is associated with a serious adverse event
- is associated with clinical signs or symptoms
- leads to additional treatment or to further diagnostic tests is considered by the investigator to be of clinical significance

Adverse Event Reporting Period

The study period during which adverse events must be reported is defined as the period from the initiation of the first study treatment to the last administration of study treatment.

Post-study Adverse Event.

All unresolved adverse events should be followed by the clinical investigator until the events are resolved, the participant is lost to follow-up, or the adverse event is otherwise explained. At the last scheduled visit, the investigator should instruct each participant to report any subsequent event(s) that the participant, or the participant's personal physician, believes might reasonably be related to participation in this study.

Abnormal Laboratory Values.

A clinical laboratory abnormality should be documented as an adverse event if the abnormality is grade 1 or more and a change from baseline.

11.1 Recording of Adverse Events.

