At each contact with the participant, the appropriately delegated and credentialed study team member must seek information on adverse events by specific questioning and, as appropriate, by examination. Information on all adverse events should be recorded immediately in the source document, and also in the appropriate adverse event module of the case report form (CRF). All clearly related signs, symptoms, and abnormal diagnostic procedures results should be recorded in the source document, though should be grouped under one diagnosis.

All adverse events occurring during the study period must be recorded. Adverse events will be measured and graded in accordance with the CTCAE. The clinical course of each event should be followed until resolution, stabilization, or until it has been determined that the study treatment or participation is not the cause. Serious adverse events that are still ongoing at the end of the study period must be followed up to determine the final outcome. Any serious adverse event that occurs after the study period and is considered to be at least possibly related to the study treatment or study participation should be recorded and reported immediately.

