11.1.1 Serious Adverse Events

Adverse events are classified as serious or non-serious.

A serious adverse event is any AE that is:

- fatal
- life-threatening
- requires or prolongs hospital stay
- results in persistent or significant disability or incapacity
- a congenital anomaly or birth defect
- Suspected transmission of an infectious agent (eg, pathogenic or nonpathogenic) via the study drug is an

The PATCH Trial
SAE.

- an important medical event

Important medical events are those that may not be immediately life threatening, but are clearly of major clinical significance. They may jeopardize the participant, and may require intervention to prevent one of the other serious outcomes noted above. For example, drug overdose or abuse, a seizure that did not result in in-patient hospitalization, or intensive treatment of bronchospasm in an emergency department would typically be considered serious. Theft, sale, or use of the study product by any person other than the participant will be reported as a medically important event.

ADVERSE EVENT COLLECTION AND REPORTING INFORMATION:

- All Serious Adverse Events (SAEs) that occur following the participant's written consent to participate in the study must be reported, whether related or not related to study drug. If applicable, SAEs must be collected that relate to any later protocol-specified procedure.
- Following the participant's written consent to participate in the study, all SAEs, whether related or not related to study drug, are collected, including those thought to be associated with protocol-specified procedures. The investigator-sponsor should report any SAE occurring after these aforementioned time periods, which is believed to be related to study drug or protocol-specified procedure.
- An SAE report should be completed for any event where doubt exists regarding its seriousness;
- If the investigator believes that an SAE is not related to study drug, but is potentially related to the conditions of the study (such as withdrawal of previous therapy or a complication of a study procedure), the relationship should be specified in the narrative section of the SAE ReportForm.

All SAEs should be followed to resolution or stabilization.

Adverse events can be spontaneously reported or elicited during open-ended questioning, examination, or evaluation of a participant. (In order to prevent reporting bias, participants should not be questioned regarding the specific occurrence of one or more AEs.)

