11.3 UPENN IRB Notification by Investigator-Sponsor

The University of Pennsylvania IRB (Penn IRB) requires expedited reporting of those events related to study participation that are unforeseen and indicate that participants or others are at increased risk of harm. The Penn IRB will not acknowledge safety reports or bulk adverse event submissions that do not meet the criteria outlined below. The Penn IRB requires researchers to submit reports of the following problems within 10 working days from the time the investigator becomes aware of the event:

- Any adverse event (regardless of whether the event is serious or non-serious, on-site or off-site) that occurs any time during or after the research study, which in the opinion of the principal investigator is:

Unexpected (An event is “unexpected” when its specificity and severity are not accurately reflected in the

Property of University of Pennsylvania
Confidential

The PATCH Trial

protocol-related documents, such as the IRB-approved research protocol, any applicable investigator brochure, and the current IRB-approved informed consent document and other relevant sources of information, such as product labeling and package inserts.)

AND

Related to the research procedures (An event is “related to the research procedures” if in the opinion of the principal investigator or sponsor, the event was more likely than not to be caused by the research procedures.)

Deaths occurring for patients on-study and within 30 days of study drug administration that are considered unforeseen and indicates participants or others are at increased risk of harm (i.e. unexpected and probably/definitely related), must be reported to the IRB within 24 hours of notification.

See: <https://irb.upenn.edu/> for additional reporting details.

11.3.1 Reporting Process to IRB at Penn.

Principal Investigators are encouraged to submit reports of unanticipated problems posing risks to participants or others using the form: “**Unanticipated Problems Posing Risks to Participants or Others Including Reportable Adverse Events**” via HS-ERA or a written report of the event within 7 working days. FDA Notification by Investigator-Sponsor.

This study is IND exempt and reporting to the FDA is voluntary using a MedWatch 3500 or via the FDA’s website for voluntary reporting.

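### All-cause death reporting is tied to a window that ends at the last dose, other sections set different windows, and the window closes at different times by arm

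*Protocol*

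**What the plan says.** Protocol section 11.2.4 sets the rule for deaths: "All deaths that occur during the protocol-specified AE reporting period (see Section 12.1), regardless of attribution, will be reported to the appropriate parties". Section 12.1 describes specimen processing and banking and contains no AE period. The period is defined in section 11.0 as "the period from the initiation of the first study treatment to the last administration of study treatment". The SAP repeats that definition for Sub-Study 3.

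Three other rules bear on a death:

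- Section 11.1.1 lists a fatal outcome as a seriousness criterion and says "All Serious Adverse Events (SAEs) that occur following the participant's written consent to participate in the study must be reported, whether related or not". No end date is given. A later sentence refers back to time periods that the section never states, and after them takes only SAEs believed related.
- Section 11.1, repeated in the SAP, calls for reporting of "Any serious adverse event that occurs after the study period and is considered to be at least possibly related" to study treatment or participation. It also requires SAEs still open at the end of the study period to be followed to their outcome.
- Section 11.3 addresses "Deaths occurring for patients on-study and within 30 days of study drug administration that are considered unforeseen", and limits these to deaths that are unexpected and probably or definitely related. They go to the ethics board within 24 hours.

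On leaving the study, section 10.3 says "Once the person is hospitalized for COVID-19 in sub-study 1 the subject is off study". In Sub-Study 3, symptomatic infection with a positive test takes a participant on HCQ off study, while a placebo participant may cross over and stay on.

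**The concern.** In a COVID-19 trial, the participants most at risk of death are those who progress or are admitted. Those are also the events at which this protocol stops study drug or ends participation. A death rule that closes at the last dose closes when the risk rises. Such deaths will usually be attributed to COVID-19, so a rule that depends on relatedness to study drug does not bring them back.

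Two consequences matter for the safety comparison. Staff applying different sections could reach different answers about the same death, so the monitoring board and the safety tables could receive incomplete mortality data. The last dose is also a post-randomization event that the crossover rule handles differently in each arm, so the arms are not observed for the same length of time.

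**Working it through.** The plan states no figure for this point. The check sets the rules side by side and follows two cases through them.

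| Rule | Opens | Closes | Deaths covered |
|---|---|---|---|
| Protocol 11.2.4 with 11.0 | First dose | Last dose | All, any attribution |
| Protocol 11.1.1 | Consent | Not stated | All fatal SAEs, related or not |
| Protocol 11.1 and SAP | After the study period | Open | At least possibly related |
| Protocol 11.3 | On study | 30 days after drug | Unexpected and probably or definitely related |

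**Case 1: admission in Sub-Study 1 (illustrative days).** Drug stops on day 3 because of a COVID-19 admission, and the participant dies on day 10 of what is judged to be COVID-19.

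1. Section 11.2.4 closed on day 3, and 10 > 3, so the death is outside it.
2. The section 11.3 window runs to day 3 + 30 = 33, and 10 < 33, but the death is not drug-related, so that rule does not apply.
3. Section 11.1 does not take it as a new event after the study period, because it is not possibly related.
4. Section 11.1.1 takes it if that section is read as having no end.
5. Otherwise it is captured if the admission was recorded as an SAE and followed to outcome. The hospitalization paragraphs under 11.1.1 exempt admission for the target disease unless the investigator judges it a worsening, so this step depends on judgment.

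The Sub-Study 1 schedule (section 9.0, Table 4) ends at release from quarantine and has no later contact for this participant.

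**Case 2: progression without admission, by arm (illustrative days).** Section 7.5 unblinds Sub-Study 1 participants for symptom progression after at least 7 days of treatment. Suppose one participant in each arm progresses on day 8.

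- HCQ: drug stops (section 5.0). The 11.2.4 window closes on day 8.
- Placebo with crossover: HCQ for up to 2 weeks (section 7.5). The window closes as late as day 8 + 14 = 22.

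The difference is up to 22 - 8 = 14 days. Sub-Study 3 has the same pattern at symptomatic infection (section 10.3): off study on HCQ, against up to 14 further days for a placebo participant who crosses over. The difference does not arise for Sub-Study 1 participants admitted before any crossover, since section 7.5 bars crossover for them.

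**Sub-Study 3 SAP.** It carries the last-dose period and the possibly-related rule for later SAEs, but neither the from-consent SAE rule of 11.1.1 nor section 11.2.4. Read alone, it has no route for an unrelated new death after the last dose.

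**The case against.** The best defense is that section 11.2.4 sets a minimum. It requires deaths within a period to be reported and does not say that later ones are not. Section 11.1.1, with no end date, can be read to cover any fatal SAE after consent. Sections 11.0 to 11.1.1 also require unresolved AEs and ongoing SAEs to be followed. Sub-Study 1 enrolls people who do not need admission, so a COVID-19 admission is naturally a worsening, hence an SAE followed to its outcome.

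This stands in part. A reader might infer that deaths are reportable only during dosing, and the documents do not support that. The defense does not settle the matter, however. Section 11.0 defines the study period as first to last dose, and section 11.1 filters new SAEs after it by relatedness, which contradicts an open-ended 11.1.1.

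Three other strong readings also fail:

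- That no contact follows the stopping of drug. Calls about co-inhabitants run to 14 days after quarantine in Sub-Study 1. Weekly calls continue for asymptomatic participants positive at one month in Sub-Study 3 (both section 8.4). Participants who choose to withdraw from treatment may continue procedures for 2 months (section 10.3). The gap is confined to those taken off study at Sub-Study 1 admission or at symptomatic Sub-Study 3 infection on HCQ.
- That section 11.3 is a competing 30-day all-cause window. It is an expedited notice with a strict relatedness filter.
- That a share of deaths missed can be stated. The background section says only that "the time from diagnosis to death can occur within one month", which gives no distribution over time.

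**Conclusion.** The point holds as a conflict between sections and a flawed window. The all-cause death rule closes at the last dose and cites the wrong section, and the neighboring rules differ in start, end and attribution. A COVID-19 death after drug is stopped is outside 11.2.4. It is reportable only through one reading of 11.1.1 or through an admission already recorded as an SAE. Two off-study groups have no scheduled vital-status check. The window can close up to 14 days earlier for an HCQ progressor than for a placebo progressor who crosses over.

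The 14 days is a maximum that assumes crossover is taken up and completed. How many deaths would be affected cannot be estimated from the documents, and mortality is not a listed endpoint in either active sub-study. This should be corrected, but it does not bear on the primary analysis.

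The protocol also says in section 11.0 that "The timely reporting of adverse events (including toxic deaths) is required by the Food and Drug Administration", while section 11.3.1 calls reporting to that agency voluntary. That is a separate, minor wording conflict.

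**What to change.** Reconcile protocol sections 11.0 to 11.3 by stating one window for deaths and SAEs of any attribution. It should run from consent to a fixed day counted from randomization, the same in both arms, and apply whether or not the participant stopped drug, crossed over or went off study. Keep the possibly-related rule after that day. Put the Sub-Study 3 window in the SAP, and correct the pointer to section 12.1.

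One example is the last scheduled dose plus 30 days: 14 + 30 = 44 days in Sub-Study 1. In Sub-Study 3 it is about 60 + 30 = 90 days on the protocol's 2 months, or 56 + 30 = 86 on the SAP's eight weeks. Either day falls after a 14-day crossover begun at the end of scheduled dosing (14 + 14 = 28; 60 + 14 = 74; 56 + 14 = 70). Section 5.0 allows up to 3 working days from randomization to first dose, so the chosen day should allow for that.

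Ascertain vital status once at that day, by chart check or phone call. The cost is wording plus one check per participant: about 100 in Sub-Study 1 and up to the 250 that section 8.4.2 expects to screen in Sub-Study 3, about 350 in all. No treatment rule changes.
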